12. SPECIFICATION OF SUBGROUPS FOR ANALYSIS

The primary efficacy endpoint will be summarized within subgroups defined by Baseline HDSS, age, gender and race/ethnicity. Adverse events and local skin reactions will be summarized by Fitzpatrick Skin Types. It is important to note that the study is not powered to demonstrate statistical significance within subgroups and therefore it is not an expectation of the analysis that statistical significance be demonstrated with the subgroups.

13. PH SUB-STUDY

13.1 Study Design and Purpose

Up to 25 total Sahara Study subjects undergoing treatment at up to 6 centers participating in the pH sub-study will be included. Select pH Sub-Study centers will commit to enrolling up to 10 subjects each into this pH Sub-Study. Enrollment can be stopped when data have been collected on at least 20 axillae (10 subjects) treated with the N-SWEAT Patch and at least 10 axillae (5 subjects) with HDSS 4 treated with the N-SWEAT patch. Centers will attempt to consent and enroll consecutive subjects into this sub-study; deviations will be documented.

The purpose of the pH Sub-Study is intended to measure the Baseline and Final Skin pH for a subset of subjects treated as part of the Sahara Study. This sub-study is designed to address a question posed by FDA regarding residual NaOH on the skin and its potential role in skin irritation or injury. NaOH is a byproduct of the N-SWEAT Patch interaction with sweat described in Section 3 in the pH sub-study protocol. In summary, the presence of sodium hydroxide results in high pH which at high enough concentrations and exposure time could be associated with skin injury; thus, measuring skin pH is a surrogate for direct measurement of sodium hydroxide concentration on the skin after treatment.

For consistency, the skin pH will be measured in both axillae. Measurements will be taken prior to treatment with the N-SWEAT Patch (or sham) and after the completion of the post-treatment cleaning as described in the Sahara Study protocol.

The pH Sub-study is designed to demonstrate that the Final Skin pH after the N-SWEAT treatment is not consistent with a level that would potentially cause skin injury. Further, the study should illustrate an absence of a significant amount of NaOH. Thus, this study will show that there is minimal risk of sustained skin exposure to significant residual NaOH following treatment with the N-SWEAT Patch.

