13.2 Timing of Analysis

Once 20 subjects have been enrolled in the pH Sub-study, a data set will be pulled to determine if at least 10 subjects/20 axilla have been treated with the N-SWEAT Patch with at least 5 subjects/10 axilla having baseline HDSS=4. If these conditions are met, enrolment into the sub-study will cease and the data will be summarized. If these conditions are not met, enrolment will continue until 25 subjects have been enrolled in the pH sub-study and the data will be summarized at this time.

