13.3 Demographics / Baseline Characteristics and Treatment Characteristics

Demographics (age, gender, race/ethnicity), baseline characteristics (HDSS, GSP, Fitzpatrick skin type, pre-treatment pH and BMI), and treatment characteristics (at a minimum, the duration of patch placement, pain level during treatment and cleaning) will be summarized by randomized group for the ITT population enrolled in the pH sub-study.

13.4 To summarize the number and percent of subjects and axilla with pH > 11 post treatment and cleaning of the area treated by randomized group

Subjects Included in Analysis: All FAS subjects will be included in the analysis.

Endpoint(s): pH after treatment and cleaning of the area treated.

Statistical Analysis: The number and percent of axilla with post-treatment pH > 11 per randomized group and per randomized group and baseline HDSS will be summarized. The number and percent of subjects with at least one axilla with post-treatment pH > 11 will be also be summarized for the same groups.

13.5 To summarize the change in pH pre to post-treatment by randomized group.

Subjects Included in Analysis: All FAS subjects will be included in the analysis.

Endpoint(s): pH pre-treatment and after treatment and cleaning of the area treated.

Statistical Analysis: Descriptive statistics for the pH pre- and post-treatment as well as the change (post treatment – pre-treatment) per axilla will be summarized by randomized group and by randomized group and baseline HDSS.

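### The pH sub-study promises to show minimal risk from residual NaOH, but it may stop at 10 treated subjects (5 with HDSS 4) and plans no interval or acceptance criterion

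*SAP*

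**What the plan says.** SAP 13.1 explains that the sub-study answers an FDA question about sodium hydroxide left on the skin, with skin pH as a surrogate. It describes the design as one that demonstrates a non-injurious final pH, and ends by saying that "this study will show that there is minimal risk of sustained skin exposure to significant residual NaOH following treatment with the N-SWEAT Patch".

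On size, the same section allows "Up to 25 total Sahara Study subjects undergoing treatment at up to 6 centers". It adds: "Enrollment can be stopped when data have been collected on at least 20 axillae (10 subjects) treated with the N-SWEAT Patch", together with "at least 10 axillae (5 subjects) with HDSS 4 treated with the N-SWEAT patch". SAP 13.2 fixes the time of the check: "Once 20 subjects have been enrolled in the pH Sub-study, a data set will be pulled". It continues: "If these conditions are not met, enrolment will continue until 25 subjects have been enrolled in the pH sub-study". The data are then summarized, with no second check of the minima.

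On analysis, SAP 13.4 plans "The number and percent of axilla with post-treatment pH > 11 per randomized group", also split by baseline HDSS, and for the same groups a count of subjects with either axilla above 11. SAP 13.5 plans descriptive statistics per axilla for pH before treatment, pH after treatment and cleaning, and the change. Under SAP Section 1 such summaries include the minimum and maximum. Nowhere does Section 13 give a hypothesis, an acceptance criterion, an interval, a precision statement or a reason for the sample size.

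**The concern.** The purpose paragraph writes a safety conclusion before there are data, and nothing in the analysis sections could confirm or refute it. If the plan is followed as written and no subject has a high pH, the report can state that minimal risk was shown without telling the reader how high a rate the data still allow.

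The unit adds to this. The size is given first in axillae, and 13.4 lists the axilla percentages before the subject count. Protocol 8.7.4 has both axillae treated at the same visit, so the two results from one person are not independent. A line reading 0 of 20 axillae looks stronger than 0 of 10 subjects, although the people are the same.

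The sub-study answers a regulator's safety question, and Protocol 8.7.2 itself warns of an alkaline or thermal burn after excessive exposure or insufficient cleaning. The strength of evidence should therefore be visible in the result.

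**Working it through.** The SAP states no precision or power figure for the sub-study, so there is none to reproduce. The check asks what zero events would rule out.

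**Inputs**
- Treated subjects at the early stop: 10, of whom 5 have HDSS 4 (SAP 13.1).
- Check at 20 enrolled, cap of 25, both arms together (SAP 13.1, 13.2).
- Allocation 1:1 (SAP Section 2), so 12 or 13 treated subjects are expected at the cap.
- Event: a subject with at least one axilla above pH 11 after treatment and cleaning (SAP 13.4).
- Confidence level: none is given for the sub-study. I assume 95%, because SAP 11.2.3.4 uses a two-sided 95% interval for the SAP's other single proportion.

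**Upper limit with 0 events in n subjects.** The exact binomial limit is 1 − 0.025^(1/n) two-sided and 1 − 0.05^(1/n) one-sided.

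| n treated | Two-sided 95% | One-sided 95% |
|---|---|---|
| 5 (HDSS 4) | 52.2% | 45.1% |
| 10 | 30.8% | 25.9% |
| 12 | 26.5% | 22.1% |
| 13 | 24.7% | 20.6% |

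For n = 10, 1 − 0.025^(0.1) = 0.3085. For n = 5, 1 − 0.025^(0.2) = 0.5218.

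**Cross-check with Wilson,** the method in SAP 11.2.3.4. The two-sided upper limit with 0 events is z²/(n + z²), with z² = 3.84. This gives 3.84/13.84 = 27.8% for n = 10 and 3.84/8.84 = 43.4% for n = 5. The conclusion is the same.

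**The same fact seen forwards.** If the true subject-level rate were 10%, the chance of no event would be 0.9^10 = 35% in 10 subjects and 0.9^5 = 59% in 5. At a true rate of 20% it would be 0.8^10 = 11% and 0.8^5 = 33%.

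**By axilla.** Even if the axillae were independent, which is optimistic, 0 of 20 gives 16.8% two-sided or 13.9% one-sided.

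**Size needed for a tighter limit.** As an illustration only, an upper limit of 10% or less with zero events needs ln(0.025)/ln(0.9), rounded up to 36 treated subjects (two-sided), or ln(0.05)/ln(0.9), rounded up to 29 (one-sided). Both exceed the cap of 25 for the two arms together.

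**Whether the minima are reached.** If each subject is assigned by an independent 1:1 draw, the chance of at least 10 treated is 59% at 20 enrolled and 89% at 25. This is an approximation, because the trial's randomization is blocked and stratified. The documents do not give the share of subjects with HDSS 4. For assumed shares of 20% to 50%, the chance of at least 5 treated HDSS 4 subjects at 25 enrolled runs from 10% to 79%. The cap can therefore be reached with one or both minima missed, and the limits would then be wider.

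**The case against.** The strongest case for the plan is that this is a small descriptive sub-study. The headings of 13.4 and 13.5 speak of summarizing, pH is called a surrogate, and no hypothesis or label claim rests on it. Study success depends on HDSS plus an acceptable safety profile (SAP Section 5). Skin reactions and adverse events are assessed directly in all randomized and roll-in subjects (SAP 6.3 and Section 10). All of this stands and limits the consequence. It does not rescue the purpose paragraph: a descriptive plan should not announce a demonstration.

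Several stronger readings are tempting, and the documents do not support them:
- *Only axillae are counted.* They are not. SAP 13.4 already plans the subject-level count for the same groups. What is missing is its priority and an interval.
- *The sub-study is fixed at 10 treated subjects.* Ten is the minimum that permits stopping at the check at 20 enrolled. More may be treated, or fewer if the cap is reached first.
- *The data can exclude only high rates of harm.* The limits above concern the dichotomy at pH 11. If post-cleaning values lie far below 11, the continuous summary in 13.5 tells more than 0 of 10 does. However, the plan attaches no interval or criterion to that summary either.
- *A single range of 26% to 52% applies.* That would join a one-sided limit for 10 subjects to a two-sided limit for 5. On one convention the pair is 31% and 52%, or 26% and 45%.

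Finally, a separate pH sub-study protocol exists and may contain a size rationale or a criterion. It is not among the documents, so the absence of an interval can be stated only of the SAP. But SAP Section 1 says that this SAP provides the sub-study's analysis plan, so its wording needs correction in any case.

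**Conclusion.** The concern holds in this form: SAP 13.1 promises a conclusion that the sample and the planned analysis cannot deliver. With no affected subject, the binary endpoint would still be compatible with a true subject-level rate of up to 31% (10 treated) and 52% (5 with HDSS 4), two-sided, or 26% and 45% one-sided. At the cap, with 12 or 13 treated, the limit is 25-26% two-sided or 21-22% one-sided. Any event would raise these figures.

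The figures rest on an assumed 95% level, the subject as unit, zero events, and independence between subjects. They say nothing on whether residual NaOH is in fact a problem; a reader should not infer that the patch leaves harmful pH, only that the sub-study could not rule it out on this endpoint. The primary efficacy result is unaffected. The point deserves correction before the sub-study is summarized, because the result goes to a regulator who asked the question.

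**What to change.** 1. In SAP 13.1, replace the language of demonstrating and showing with a descriptive aim: to describe skin pH after treatment and cleaning.
2. In SAP 13.4, name the subject-level count (at least one axilla above pH 11) as the main result, and report its exact 95% confidence limit by arm and for HDSS 4, stating whether it is one- or two-sided. Keep the per-axilla counts as supportive, with a note that two axillae of one subject are not independent.
3. Report the 13.5 summary of continuous pH alongside, including the maximum post-treatment value.
4. Do not write a fixed excluded rate into the SAP. The limit depends on the number treated and the number of events, and differs between all treated subjects and those with HDSS 4.

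The cost is a few sentences and one confidence limit per table row. No extra subjects, visits or measurements are needed. The downside for the sponsor is that the stated conclusion becomes less favourable.

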13.2 Timing of Analysis

Once 20 subjects have been enrolled in the pH Sub-study, a data set will be pulled to determine if at least 10 subjects/20 axilla have been treated with the N-SWEAT Patch with at least 5 subjects/10 axilla having baseline HDSS=4. If these conditions are met, enrolment into the sub-study will cease and the data will be summarized. If these conditions are not met, enrolment will continue until 25 subjects have been enrolled in the pH sub-study and the data will be summarized at this time.

13.3 Demographics / Baseline Characteristics and Treatment Characteristics

Demographics (age, gender, race/ethnicity), baseline characteristics (HDSS, GSP, Fitzpatrick skin type, pre-treatment pH and BMI), and treatment characteristics (at a minimum, the duration of patch placement, pain level during treatment and cleaning) will be summarized by randomized group for the ITT population enrolled in the pH sub-study.

13.4 To summarize the number and percent of subjects and axilla with pH > 11 post treatment and cleaning of the area treated by randomized group

Subjects Included in Analysis: All FAS subjects will be included in the analysis.

Endpoint(s): pH after treatment and cleaning of the area treated.

Statistical Analysis: The number and percent of axilla with post-treatment pH > 11 per randomized group and per randomized group and baseline HDSS will be summarized. The number and percent of subjects with at least one axilla with post-treatment pH > 11 will be also be summarized for the same groups.

13.5 To summarize the change in pH pre to post-treatment by randomized group.

Subjects Included in Analysis: All FAS subjects will be included in the analysis.

Endpoint(s): pH pre-treatment and after treatment and cleaning of the area treated.

Statistical Analysis: Descriptive statistics for the pH pre- and post-treatment as well as the change (post treatment – pre-treatment) per axilla will be summarized by randomized group and by randomized group and baseline HDSS.
